The authors previously reported that, when an early recovery program was applied after laparoscopic right hemicolectomy for right-sided colon cancer, the end-to-side anastomosis group had a higher cumulative recovery rate on postoperative day 7 (71.7% vs. 93.0%, $p = 0.019$), a shorter length of hospital stay (7 vs. 6 days, $p = 0.003$), and a lower complication rate (26.1% vs. 4.6%, $p = 0.008$) compared to the side-to-side anastomosis group (7). Another study reported that side-to-side anastomosis was a major factor contributing to early recovery program failure in patients, including those with not only right-sided colon cancer but also left-sided and sigmoid colon cancer (8).

2) Hypothesis and purpose

Currently, there is no established standard anastomotic technique for laparoscopic right hemicolectomy. End-to-side anastomosis is considered anatomically ideal, and it is hypothesized that it may result in superior short-term outcomes. This study aims to demonstrate the superiority of end-to-side anastomosis through a prospective randomized comparative study between end-to-side and side-to-side anastomosis.

9. Investigational Drug and Medical Device Code Name (or Generic Name of Active Ingredient), Quantity of Active Ingredient, Dosage Form (Including Comparator) : Not applicable.

10. Selection Criteria, Exclusion Criteria, Target Sample Size, and Rationale for Sample Size Calculation

1) Selection Criteria:

Subjects must meet all of the following conditions:

① Patients with right-sided colon cancer

Right-sided colon cancer is defined as tumors located from the cecum to the hepatic flexure. The histological type is limited to adenocarcinoma.

- ② Patients aged between 18 and 80 years
- ③ Patients with adequate bone marrow function:
Hemoglobin ≥ 10 g/dL (in cases of simple iron deficiency anemia, correction is required)
White blood cell count $\geq 4,000/\text{mm}^3$
Platelet count $\geq 100,000/\text{mm}^3$
- ④ Patients with adequate renal function (Creatinine ≤ 1.5 mg/dL)
- ⑤ Patients without significant functional impairment of the heart, lungs, or other major organs
- ⑥ Patients who have signed the written informed consent form

2) Exclusion Criteria

Patients who meet any of the following conditions will be excluded from this clinical trial:

- ① **Patients with distant metastasis or local invasion to the small intestine, ureter, or other adjacent structures requiring combined resection**

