- ② **Patients in whom laparoscopic surgery is not feasible due to a history of prior abdominal surgery or the severity of the disease**
- ③ **Patients requiring emergency surgery due to bowel obstruction or peritonitis**
- ④ **Patients taking other oral medications for bowel movement disorders, such as chronic constipation, before surgery**
- ⑤ **Patients with severe cardiopulmonary disease, mental illness, or other comorbidities that prevent the application of the early recovery program**
- ⑥ **Patients who do not consent to the study or do not sign the informed consent form**
- ⑦ **Patients deemed ineligible for clinical trial participation based on the physician's judgment**

3) Target Sample Size and Rationale for Sample Size Calculation

This study aims to evaluate the superiority of end-to-side anastomosis over side-to-side anastomosis in terms of short-term outcomes. The sample size was calculated based on previous studies (7,9).

Allocation ratio: 1:1

Type I error (α): 5%

Power: 80%

Expected difference in 7-day cumulative recovery rate: 20% (End-to-side: 90% vs. Side-to-side: 70%)

Expected dropout rate: 10%

The calculated sample size is as follows:

◆ Target number of participants: 130

End-to-side anastomosis group: 65 participants

Side-to-side anastomosis group: 65 participants

(The sample size will be further reviewed and adjusted upon consultation with the Clinical Research Institute at Seoul National University.)

◆ Randomization

The **allocation ratio** between groups will be **1:1**.

The anastomosis method will be determined preoperatively using a **random table or computer-generated randomization program**.

Group allocation will be revealed **in the operating room just before anastomosis**.

(The randomization process will be conducted in consultation with the Clinical Research Institute at Seoul National University.)

4) Recruitment Plan

There will be **no public recruitment announcement** for participant enrollment. Instead, patients admitted for **laparoscopic right hemicolectomy** for right-sided colon cancer will be provided with detailed information about the study, including its objectives, safety, and potential risks. After obtaining written informed consent, eligible patients will be enrolled in the study.

11. Study methods

1) Detailed methods

(1) Design

: Prospective randomized clinical trial

(2) Classification of Patient Groups

① **Patient group classification will be revealed just before surgery.**

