Postoperative Day 2	Soft porridge (three times a day)	There is no strict limitation on the amount, but if symptoms such as nausea, vomiting, or abdominal pain occur, discontinue the diet and perform necessary examinations and treatments.	Walking in the hospital corridor: Walk back and forth along the corridor at least three times. If walking alone is difficult, assistance from a caregiver or the use of a walker is allowed.
After Postoperative Day 2	Soft porridge (three times a day)	There is no strict limitation on the amount, but if symptoms such as nausea, vomiting, or abdominal pain occur, discontinue the diet and perform necessary examinations and treatments.	Walking in the hospital corridor: Walk back and forth along the corridor at least three times. If walking alone is difficult, assistance from a caregiver or the use of a walker is allowed.

Table 1. Implementation of the Early Recovery Program

(4) Data Collection Items

- ① **Basic patient data** (age, sex, body mass index, medical history, ASA grade)
- ② **Preoperative staging** (CT, endoscopic findings)
- ③ **Intraoperative findings** (operative time, intraoperative blood loss)
- ④ **Postoperative course** (gas out time, length of hospital stay, recovery time, occurrence of complications)
- ⑤ **Histopathological results and staging**
- ⑥ **Readmission within one month after surgery and its reason**

2) Control Group Setting and Randomization Method

A comparison will be made between end-to-side anastomosis and side-to-side anastomosis.

Randomization will be conducted using the **SAS program**, managed by the **MRCC at Bundang Seoul National University Hospital**. A random number will be generated, assigned a serial number, and the anastomotic method will be delivered just before surgery to ensure random allocation.

3) Investigational Drug Administration/Usage, Method of Administration, Concomitant Therapy, and Justification for Comparator Use

Not applicable.

4) Observation Items, Clinical Examination Items, and Evaluation Methods for Study Outcomes

(1) Primary Endpoint: 7-Day Cumulative Recovery Rate

The **cumulative recovery rate** is defined as the percentage of patients who have reached **recovery time** within a specific postoperative period.

The definition of **recovery time** is based on previous studies by the investigators (7, 9) and is defined as the postoperative time at which **all** of the following conditions are met:

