- ① **No issues for 24 hours after diet initiation** (at least one-third intake of liquid diet or higher).
- ② No additional analgesic administration after discontinuation of patient-controlled analgesia (PCA).
- ③ No major complications and stable afebrile condition (body temperature $\leq 37.2^{\circ}\text{C}$).
- ④ No issues with ambulation (ability to walk a distance of at least 600 meters).

(2) Secondary Endpoint

- **Length of hospital stay**
- **Complications**
- **Failure rate of the early recovery program**
- **Readmission rate within one month after surgery**

5) Criteria and Methods for Efficacy Evaluation

This study evaluates the superiority of end-to-side anastomosis over side-to-side anastomosis in terms of short-term outcomes. The sample size was calculated based on previous studies (7,9).

- **Allocation ratio:** 1:1
- **Type I error (α):** 5%
- **Power:** 80%
- **Expected difference in 7-day cumulative recovery rate:** 20% (End-to-side: 90% vs. Side-to-side: 70%)
- **Expected dropout rate:** 10%

The hypothesis to be tested is that the **cumulative recovery rate** in the end-to-side anastomosis group is 20% higher than in the side-to-side anastomosis group.

6) Differences from Existing Treatments and Studies

Both **end-to-side and side-to-side anastomosis** are standard anastomotic techniques commonly used in clinical practice, meaning that this study does not involve a new or experimental treatment. However, research specifically comparing **anastomotic techniques in right-sided colon cancer** is limited, with most existing studies being retrospective cohort studies. Thus, this study will be the first prospective, randomized controlled trial investigating anastomotic methods in right-sided colon cancer.

7) Benefits and Risks for Study Participants

Since this study compares two **existing standard anastomotic techniques**, there are minimal risks or additional benefits associated with participation. Furthermore, the scientific and medical knowledge gained from this research is expected to far outweigh any potential risks or **adverse effects** experienced by study participants.

8) Discontinuation and Withdrawal Criteria

- ① Conversion to open surgery during the procedure due to safety concerns that make continued laparoscopic surgery unsafe for the patient.
- ② Participants who initially consented to the study but later decide to withdraw their consent.

9) Criteria, Methods, and Reporting for Adverse Events and Safety Evaluation

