B. Safety review will be conducted as follows to determine study modification or termination:

- If a serious and unexpected adverse event occurs:
 - (A) The principal investigator will review the event and decide on study modification or termination.
 - (B) If the IRB review results in a decision to modify or terminate the study, the research team will comply with the IRB's directive.
- Safety review will be conducted once every 6 months:
 - (A) The principal investigator will review all adverse events that occurred in the past 6 months and determine whether study modification or termination is necessary.
 - (B) The findings reviewed in section (A) will be reported as an "Other Report" to the respective Institutional Review Board (IRB) of each institution.

11) Data Analysis and Statistical Methods

- Statistical analysis will be conducted using SPSS or STATA. A p-value of ≤ 0.05 will be considered statistically significant.
 - Continuous variables: Student's t-test, Mann-Whitney U test
 - Binary variables: χ^2 -test, Fisher's exact test
- If advanced statistical analysis techniques are required, consultation with the Medical Research Institute will be sought for expert statistical guidance and analysis.

12) Study Schedule

Contents	Duration											
	2	4	6	8	10	12	14	16	18	20	22	24
IRB Review	■											
Selection of Study Participants and Obtaining/Registration of Informed Consent		■	■	■	■	■	■	■				
Data collection			■	■	■	■	■	■				
Statistical analysis									■	■		
Final Report										■	■	
Final Research Paper										■	■	

12. Measures for the Protection of Study Participants' Safety

1) Basic Measures to Ensure Ethical Conduct of the Study

- The study will comply with the Declaration of Helsinki (2013 revision) and ICH-GCP guidelines.
- The study will be conducted only after obtaining IRB approval.

2) Informed Consent Process for Study Participants

- ① Researchers responsible for explaining the study and obtaining consent: A physician among the research team.
- ② Individuals providing consent: Study participants.
- ③ Waiting period between study explanation and consent acquisition: 20 minutes.
- ④ Methods to minimize coercion or undue influence:
 - a. The researcher (usually the attending physician) will explain the study to the participant.
 - b. The research coordinator will provide additional explanations in a separate space.
 - c. The researcher will confirm if the participant has any additional questions before obtaining consent.

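### Does leaving the primary test unnamed (chi-square or Fisher) cost the trial its planned 80% power?

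*Combined protocol and SAP*

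**What the plan says.** The primary endpoint in Section 11.4 is "1) Primary Endpoint: 7-Day Cumulative Recovery Rate", the percentage of patients who have met all recovery criteria by day 7, so it is a binary outcome. Section 11.11, like the Study Overview table, lists tests by type of variable: "Binary variables: χ^2 -test, Fisher's exact test". The decision rule is "A p-value of ≤ 0.05 will be considered statistically significant". Neither place ties a test to the primary endpoint, mentions a continuity correction or states sidedness.

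Section 10.3 gives the planning inputs: 1:1 allocation, alpha 5%, power 80%, 90% versus 70%, 10% dropout, and 130 patients (65 per arm). It names no formula or test. Section 11.5 repeats these inputs, except the total, and words the hypothesis as the recovery rate "in the end-to-side anastomosis group is 20% higher than in the side-to-side anastomosis group", which is the planning difference and not a null hypothesis.

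The background section reports the investigators' earlier comparison of the same two techniques: "cumulative recovery rate on postoperative day 7 (71.7% vs. 93.0%, $p = 0.019", and "a lower complication rate (26.1% vs. 4.6%, $p = 0.008". It gives neither group sizes nor the tests used.

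**The concern.** Two tests are listed, and one of them (chi-square) comes with or without a continuity correction. At about 60 patients per arm these versions do not agree closely. If the sample size was set for the uncorrected test and the analysis uses a more conservative one, the trial falls short of 80% power at its own assumptions. If the test is picked after the data are seen, a borderline result could be called superior or not at will.

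The earlier p-values seem to make this more than theoretical. On the group sizes that best fit the printed percentages, neither p-value comes from the uncorrected chi-square. That suggests the investigators habitually use the tests for which 130 patients are too few.

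**Working it through.** **Inputs.** Rates 0.90 and 0.70, alpha 5%, power 80%, dropout 10%, 65 per arm (Section 10.3). Evaluable per arm: 65 × 0.9 = 58.5, so 58 or 59. Sidedness is not stated; two-sided is assumed first and one-sided is shown afterwards.

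**1. The plan's sample size.** Two-sided, unpooled variance:

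n = (1.96 + 0.8416)² × (0.9×0.1 + 0.7×0.3) / 0.2² = 7.849 × 0.30 / 0.04 = 58.87, so 59 per arm.

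Allowing for dropout, 59 × 1.1 = 64.9, so 65 per arm and 130 in total. (Dividing instead, 59/0.9 = 65.6, gives 66 per arm and 132.) The stated size is reproduced. It is not the only route: a one-sided 5% formula with continuity correction gives 57.97, so 58, and 58/0.9 = 64.4, so again 65 per arm. The two-sided pooled formula gives 62 before and 69 after dropout; with continuity correction it gives 72 and 80.

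**2. Exact power.** Both binomial distributions (0.90 and 0.70) are enumerated, and the probabilities of all tables with p ≤ 0.05 are summed.

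| Evaluable per arm | Chi-square, uncorrected | Chi-square, corrected | Fisher |
|---|---|---|---|
| 58, two-sided | 79.7% | 71.0% | 71.6% |
| 59, two-sided | 80.5% | 72.0% | 72.0% |
| 65, two-sided | 83.2% | 77.5% | 77.5% |
| 58, one-sided 5% | – | 81.8% | 81.8% |
| 65, one-sided 5% | – | 85.7% | 85.7% |

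**3. How often the choice decides the result.** Under two-sided testing, uncorrected and corrected tests disagree in 79.72 − 70.98 = 8.74% of trials at 58 per arm and 83.17 − 77.54 = 5.63% at 65. Example: 50/58 versus 41/58. With N = 116, the cross-product difference is 50×17 − 41×8 = 522, and chi-square = 116 × 522² / (58 × 58 × 91 × 25) = 4.13, p = 0.042. With the correction, 522 − 58 = 464, chi-square = 3.26, p = 0.071. Fisher gives p = 0.070.

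**4. Would the usual small-cell rule call for Fisher?** With 80% recovering overall, the smallest expected count is 0.2 × 58 = 11.6, or 0.2 × 65 = 13. At 90% versus 70% and 58 per arm, an expected count below 5 occurs in about 0.017% of trials.

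**5. The earlier p-values.** Denominators are not given. The best fit is 46 and 43 patients: 33/46 = 71.7% versus 40/43 = 93.0% recovered, and 12/46 = 26.1% versus 2/43 = 4.65% with complications.

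| Outcome | Printed p | Uncorrected | Corrected | Fisher | Smallest expected count |
|---|---|---|---|---|---|
| Recovery | 0.019 | 0.0090 | 0.0194 | 0.0121 | 7.73 |
| Complications | 0.008 | 0.0055 | 0.0130 | 0.0075 | 6.76 |

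Recovery matches only the corrected chi-square, and complications match only Fisher. The complication match needs 4.65% to have been printed as 4.6%, which is truncation; under strict rounding no denominator fits both end-to-side percentages.

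**6. Sensitivity to the planning rates.** At the earlier study's own rates (93.0% versus 71.7%) and 58 per arm, two-sided power is 88.6%, 82.2% and 82.3% for the uncorrected, corrected and Fisher tests.

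**The case for a change.** The strongest case for a change is that the gap is real and cheap to close. One of the candidate tests meets the stated power and two miss it by 8 to 9 points at the expected dropout, and by 2.5 points even with none. Between 5.6% and 8.7% of trials would be significant by one test and not by another. A sentence written before analysis would remove the choice. The unwritten convention of Fisher for sparse cells does not settle the continuity correction, and the earlier complication result, with expected counts above 5, does not seem to have followed it.

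Most of the arithmetic stands. The inference drawn from it is weaker. The shortfall needs two-sided testing, which the plan does not state. The stated aim is directional, and at one-sided 5% the conservative tests exceed 80%. (If the inferred counts are right, the earlier p-values were two-sided, so the two-sided reading remains the more likely one.) The precedent points to two different tests for two similar outcomes, so there is no single habitual test to carry forward. It rests on inferred counts, and the recovery p-value may come from a time-to-event test. No section says the earlier methods will be reused. Nor is the uncorrected test beyond argument: at a common rate of 80% its two-sided type I error is 5.3% at 58 per arm and 4.9% at 65, so an analyst who prefers a more conservative test can defend that.

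What remains is that the test, the correction and the sidedness are not written down.

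**Conclusion.** The omission is genuine, but it is missing detail and not a fault in the design. Read in the ordinary way, the listed tests mean chi-square for the primary endpoint, with Fisher's test for a sparse table that will almost never occur here. Without a continuity correction, that analysis gives two-sided power of 79.7% to 83.2% for 58 to 65 evaluable patients per arm, which agrees with the stated 80% and with a standard derivation of 130. Naming it would record a test the plan already lists and would alter neither the size nor the conduct of the trial.

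The lower figures, 71.0% to 77.5%, hold only if testing is two-sided at 5%, the true rates are exactly 90% and 70%, and the corrected or Fisher test is used. The earlier p-values are suggestive on the last point but cannot establish it, and they give no ground for enrolling more patients. The residual risk is a borderline result whose significance depends on the test, at most about 9% of trials under the planning assumptions. A reader of the results can check for that by looking at which test is reported.
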